no events. We stratified the patients as being high risk for cardiac events if they had history of IHD, peripheral artery disease (PAD), or underwent a PAD-related operation. We ultimately collected information on 171,357 patients who underwent the target operations and were included in our analysis.

FIGURE 2. Probability of the Composite Endpoint at Various Levels of the Postoperative Nadir Hb – Multicenter data

Similarly to the single institutional analysis, a strong association was seen between increasing values of nadir postoperative Hb and freedom from the composite endpoint (OR: 0.566, 95% CI: 0.561 to 0.57, Figure 2). From the initial patient pool, 38,153 patients were at high risk for cardiac events and dropped their nadir postoperative Hemoglobin in the early postoperative period below 10 gm/dl, conditions that would make them eligible for the proposed trial. In this high cardiac risk patient population, the composite outcome occurred in almost 30% of patients with nadir Hb between 6-9 gm/dl (a subset that will represent the restrictive transfusion arm in the proposed study) and in 15% of patients with nadir Hb between 9-10 gm/dl (a subset that will represent the liberal transfusion arm in the proposed trial). Event rates for the composite and individual endpoints are summarized in TABLE 2 below:

TABLE 2. Composite Event Rates and Individual Event Rates among Veterans at High Cardiac Risks after a Surgical Procedure

Nadir Hb	Composite Endpoint	Death	MI	ARF	Coronary Revascularization
6-9 gm/dl	29.5%	15.3%	11.0 %	11.1%	0.4%
9-10 gm/dl	15.0%	6.9%	6.2%	4.1%	0.3%

III. SIGNIFICANCE AND RELEVANCE TO VETERANS

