Assessment of one year mortality will be performed as part of a passive follow up performed by the Chairman's office via examination of the electronic medical record, follow up phone calls, and search of national databases documenting mortality.

FIGURE 3: Study Flow

VII. PARTICIPANT POPULATION

All Veterans who are scheduled to undergo vascular or general surgery at a VAMC will be invited to participate in this trial. The inclusion and exclusion criteria are outlined below.

A. Inclusion Criteria

- 1) Male and female Veterans older than 18 years of age who have postoperative Hb < 10gm/dl within 15 days after the index operation
- 2) Patients undergo an operation in either one of the three following categories
 - a. Veterans who undergo PAD – related operations including but not limited to the following: aortobifemoral or aortobiiliac bypass, open abdominal aortic aneurysm repair with simultaneous repair of aortoiliac occlusive disease, visceral bypass, iliofemoral bypass, femoral bypass or endarterectomy, infrainguinal bypass; thromboembolectomy; supra-aortic trunk bypass or endarterectomy, carotid endarterectomy, and major lower extremity amputations (transfemoral, through the knee, or transtibial)

- b. Veterans with past medical history of ischemic stroke/TIA of likely carotid origin, or history of IHD (defined as known prior MI, EKG findings consistent with prior MI, prior percutaneous coronary intervention, prior coronary artery bypass surgery, history of angina for which the patient is currently receiving treatment, or stress test indicating myocardial ischemia), or history of PAD (defined as prior intervention for PAD or ABIs < 0.9) who undergo the following General Surgery operations: Open cholecystectomy or other open complex biliary reconstruction (such as open common bile duct exploration for stones, reconstruction as part of oncologic operations such as palliative pancreatic cancer procedures), open or laparoscopic small bowel resection, pancreatectomy, colon resection, colostomies (reversals and takedowns), intestinal anastomosis takedown and revision, rectal resection, splenectomy, transhiatal esophagectomy, liver resection, gastric operations (resections or repairs), gastric bypasses, adrenalectomy, major diaphragmatic hiatal hernia repair, Nissen funduplications, and ventral hernia repair

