The active follow up period for study purposes will be up to 90 days after randomization. If the participant refuses to continue participation during active follow up, his or her participation in the study will be terminated. All participants who complete the active follow-up phase of the study will be followed up to one year by the Chair's Office to assess mortality using a combination of phone call follow-up, search of the DAF, or electronic medical record

assessment. If a participant declines to participate in long term follow up then one year mortality data for this participant will not be collected. Given that the one year follow up is passive and does not involve any participant action we do not anticipate this to become a major issue.

X. TRANSFUSION STRATEGIES

Participants will be randomized to a liberal (transfuse if Hb <10 gm/dl) or restrictive (transfuse if Hb <7gm/dl) transfusion groups. Transfusion will be administered in order to maintain Hb just above the aforementioned thresholds for the index hospital stay or up to 30 days after randomization, whatever comes first. A participant must be randomized within 24-hrs of the first postoperative Hb falling below 10 gm/dl. It is strongly recommended that the transfusion treatment is initiated as soon as possible after and no longer than 24 hours from identifying a protocol-required transfusion Hb threshold. Transfusions will be administered according to the following scheme.

- A. Liberal group (transfusion trigger: Hb < 10 gm/dl)
 - i. If Hb < 7.5 gm/dl transfuse three units PRBCs, then check Hb. Based on the return Hb value, follow the transfusion protocol (steps i, ii, or iii) until Hb \geq 10.
 - ii. If $7.5 \leq$ Hb < 8.5 gm/dl transfuse two units PRBCs, then check Hb. Based on the return Hb value, follow the transfusion protocol (steps i, ii, or iii) until Hb \geq 10.
 - iii. If Hb \geq 8.5 gm/dl transfuse one unit PRBCs, then check Hb. Based on the return Hb value, follow the transfusion protocol (steps i, ii, or iii) until Hb \geq 10.
- B. Restrictive group (transfusion trigger: Hb < 7 gm/dl)
 - i. If Hb < 5.5 gm/dl transfuse of two units PRBCs, then check Hb. Based on the return Hb value, follow the transfusion protocol (steps i, or ii) until Hb \geq 7.
 - ii. If $5.5 \leq$ Hb < 7 gm/dl transfuse one unit PRBCs, then check Hb. Based on the return Hb value, follow the transfusion protocol (steps i, or ii) until Hb \geq 7.

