Participant Hb, creatinine, and troponin levels will be collected on days 1, 2, 3, 4, and 7 post-randomization or discharge (whatever is shortest). EKG will be performed on days 1 and 4 after randomization. If a participant is discharged prior to post-randomization day 4, EKG will be obtained at discharge. Results on Hb (standard of care/per transfusion protocol requirements), creatinine, troponin, and EKG performed at other time points will also be collected until discharge as supporting documentation for endpoint adjudication. If available at the institution, CK-MB will also be collected (not required).

Urine output will also be monitored in patients admitted to the Intensive Care Unit and it will be reviewed daily by the Study Coordinator. If the patient has anuria for more than 12 hours, or has urine output less than 0.3 ml/Kg/hr for more than 24 hours then the urine output will be documented as evidence for the development of ARF.

Hemoglobin and transfusion record: We will record the number of blood transfusions during the preoperative, intraoperative, and postoperative time periods. The protocol requires that Hb levels be measured on day of randomization, days 1,2,3, and 4 after randomization as well as on day 7 if the participant remains in the hospital. Hb measurements, performed as standard clinical practice, will also be recorded. The Site Coordinator will record information on a) preoperative, intra-operative, and postoperative transfusions, and b) Pre- and post-randomization Hb levels. Information on Hb levels and transfusions will be obtained by contacting the hospital laboratory directly or from the chart. Information on transfusions will be obtained from the chart and the blood bank.

XI. MONITORING AND REPORTING SERIOUS ADVERSE EVENTS

A. Importance of Serious Adverse Event Reporting

Timely and complete reporting of safety information assists study management in identifying any untoward medical occurrence, thereby allowing: a) protection of safety of study participants, b) a greater understanding of the overall safety profile of the study treatments and therapeutic modalities, c) improvements in study design or procedures, and d) compliance with regulatory requirements.

B. Role of the Local Site Investigator in Serious Adverse Event Monitoring

The local site investigator, as well as other site personnel, shall be personally responsible for the following requirements:

1. Closely monitoring all study participants for new SAEs;

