In order to estimate 90 day composite endpoint rate (defined in Section V) after surgical interventions in the VA population, we conducted an analysis of Vascular and General Surgery operations identical to those targeted in the proposed trial as described in pages 5-7. Data of 171,357 VA patients who underwent these vascular or general procedures and had available nadir Hb level from the Corporate Data Warehouse (CDW) database was used for this analysis. We anticipate in the proposed trial the nadir Hb in the restrictive transfusion group to range between 6-9 gm/dl (transfusion trigger Hb < 7 gm/dl). Our database review revealed that 29.8% out of 25,343 patients who were at high cardiac risk and had nadir postoperative Hb at this range developed the composite endpoint of death, MI, acute renal failure, or coronary revascularization within 90 days from the index operation. The breakdown of event rates for the individual components of the composite endpoint is shown in Table 2 . Based on the analysis, a baseline event rate of 30% for the composite endpoint is expected in the restrictive group.

B. Sample Size Calculation and Power Analysis

The sample size estimation and power analysis are based on the hypothesis testing of the primary composite endpoint, which is the most important measure proposed in the study. According to the analysis of event rates outlined in the previous section, we assume that 30% rate for the primary endpoint can be anticipated in the restrictive transfusion group. We also assume a 25% reduction or 22.5% event rate in the liberal group. The sample size for the study is estimated based on a superiority trial design. To detect the expected 7.5 percentage point difference or 25% reduction, a sample size of 1444 will be required at 90% power, 5% type-I error rate and with a two-sided test (TABLE 3). Assuming 5% dropout rate, then 1520 participants (or 760/group) will be needed to achieve the desired testing power.

TABLE 3 Sample Size Estimation and Power Analysis

90 Day Composite Endpoint (%)				Power (%)			
Liberal	Restrictive	Difference	Percent Difference	75	80	85	90
17.50	25.00	7.50	30.0	826	932	1066	1248
18.75	25.00	6.25	25.0	1214	1372	1570	1836
20.00	25.00	5.00	20.0	1936	2188	2502	2928
21.00	30.00	9.00	30.0	650	734	840	982
22.50	30.00	7.50	25.0	954	1080	1234	1444
24.00	30.00	6.00	20.0	1520	1718	1964	2298
24.50	35.00	10.50	30.0	526	594	678	794

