The primary study endpoint will be composite outcome of all-cause mortality, MI, coronary revascularization, acute renal failure, or post-randomization stroke within 90 days from randomization. This outcome will be compared according to assigned transfusion strategy (analysis by intent to treat), using Pearson χ^2 test. The test for differences between transfusion strategies in the primary outcome will be conducted at an overall α -level of 0.05. Additional analysis will be conducted using logistic models to adjust for other clinical factors, such as age, RCRI, nadir Hb, and interaction terms. Logistic regression will be used for the primary endpoint ($y = 1$ if a composite outcome, otherwise $y = 0$) analysis with transfusion strategy group as the testing factor (X). The following covariates will be included in the model: age (z_1), RCRI (z_2), nadir Hb(z_3), site (z_4), and the interactions of testing factor with age (w_1), RCRI (w_2) and nadir Hb (w_3). Given the composite outcome probability $p = \Pr(y=1|X, z_1, z_2, z_3, z_4, w_1, w_2, w_3)$, the basic model is defined as follows:

$$\text{Logit}(p) = \ln\left(\frac{p}{1-p}\right) = \beta_0 + \beta_1 X + \beta_2 z_1 + \beta_3 z_2 + \beta_4 z_3 + \beta_5 z_4 + \beta_6 w_1 + \beta_7 w_2 + \beta_8 w_3$$

Odds ratio and 95% confidence interval (CI) will be presented using SAS PROC GENMOD. If the coefficient for treatment effect is significant, then the null hypothesis will be rejected. Logistic models will be tested for goodness of fit. We will assess goodness-of-fit using the statistic -2 log likelihood, which has a chi-square distribution under the null hypothesis that all the explanatory variables in the model are zero. We will also consider the Akaike Information Criterion statistic and the Schwartz Criterion statistic, both of which adjust the -2 log likelihood for the number of items in the model. Models that show lack of fit will be reconsidered for the inclusion of additional variables or use of alternate models with assumptions that are better met by the study data. One alternate model if model fit is poor for logistic regression is a log-linear model.

3. Secondary endpoint analyses

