7.1. Primary Endpoint Analysis

The primary study endpoint will be a composite outcome of all-cause mortality, MI, coronary revascularization, acute renal failure, or post-randomization stroke within 90 days from randomization. A clinical events committee will adjudicate all component events for the primary endpoint. The number and percentage of participants with the composite endpoint at the 90-day visit after the randomization will be summarized and compared according to assigned transfusion strategy (analysis by intent to treat) using Pearson χ^2 test. Another analysis will compare primary endpoint between the two transfusion strategies stratified by clinical sites using the Cochran-Mantel-Haenszel test (Table 16a-e). The test for differences between transfusion strategies in the primary outcome will be conducted at an overall α -level of 0.05. Additional analysis will be conducted using logistic models to adjust for other clinical factors, such as age, RCRI, and nadir Hb. The interactions of the intervention with age, RCRI and nadir Hb will also be considered.

Odds ratio and 95% confidence interval (CI) will be presented using SAS PROC GENMOD or PROC LOGISTIC. Assumptions of the model including linearity in the logit of the composite event risk for continuous variables will be checked. We will assess goodness-of-fit using the statistic -2 log likelihood, which has a chi-square distribution under the null hypothesis that all the explanatory variables in the model are not associated with the outcome

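### The adjusted treatment models use nadir Hb with no time window; on the likelier reading it is a post-randomisation variable that the assigned trigger is meant to change, so the adjusted OR or HR does not estimate the effect of the assigned strategy

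*SAP*

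**What the plan says.** SAP 7.1 describes the supportive model for the primary endpoint: "Additional analysis will be conducted using logistic models to adjust for other clinical factors, such as age, RCRI, and nadir Hb". Protocol XVI.E.2 is similar, "to adjust for other clinical factors, such as age, RCRI, nadir Hb, and interaction terms", and writes out a treatment-by-nadir interaction. SAP 7.2, 7.3 and the time-to-event part of 7.4 carry the covariate into the secondary, tertiary and Cox models (Tables 17, 19, 21, 23, 27 and 28; protocol Table 4). SAP 7.1 also tells the analyst to reject the adjusted null for the intervention when its coefficient is significant.

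No section gives nadir Hb a time window. The SAP abbreviation list expands nHb only as a postoperative nadir, with no cut-off at randomisation. Three protocol sections bear on its timing:

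- XVI.A: "We anticipate in the proposed trial the nadir Hb in the restrictive transfusion group to range between 6-9 gm/dl", with that arm's trigger given beside the range.
- II.c refers to patients with "nadir Hb between 9-10 gm/dl (a subset that will represent the liberal transfusion arm in the proposed trial".
- X: "Transfusion will be administered in order to maintain Hb just above the aforementioned thresholds for the index hospital stay", or for up to 30 days after randomisation if that comes first.

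**The concern.** A covariate in a randomised comparison should be fixed before assignment. If the nadir includes later values, the intervention acts on it directly, and two things follow.

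1. **The estimand changes.** Any benefit of liberal transfusion that works by keeping Hb up is assigned to the nadir term and taken out of the treatment coefficient. An adjusted OR near 1 would then not mean that the strategy does little.
2. **Bias appears.** Sicker patients tend to have both a lower nadir and more events. At the same nadir, a liberal-arm patient is on average sicker than a restrictive-arm patient, because transfusion has held the value up. The coefficient moves towards apparent harm from the liberal strategy even when there is no effect.

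These estimates will be reported beside the unadjusted results for the primary, secondary and tertiary endpoints in five analysis populations. In the Cox models, a nadir recorded after the event adds a timing problem.

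**Working it through.** **1. The plan's own figure.** Inputs from SAP 4.5: 30% and 22.5%, two-sided 5%, 90% power, 5% dropout. With pooled rate 0.2625:

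n per arm = [1.960·√(2·0.2625·0.7375) + 1.282·√(0.30·0.70 + 0.225·0.775)]² / 0.075² = 722 after rounding up.

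The total is 1444, and 1444/0.95 = 1520, as stated. The implied OR is (0.225/0.775)/(0.30/0.70) = 0.677. The chi-square test does not use nadir Hb, so none of this changes.

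**2. Which nadir is meant.** A value fixed before randomisation can differ between arms only by chance. XVI.A and II.c expect 6-9 gm/dl for the restrictive arm and 9-10 gm/dl for the liberal arm, which can arise only after assignment. SAP 6.4 and Table 11 list pre-operative Hb as the baseline Hb, not a nadir. SAP 5.3 defines baseline as the last value before randomisation, not the lowest.

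**3. How far the arms could separate.** All participants "have postoperative Hb < 10gm/dl within 15 days after the index operation", so a nadir already reached cannot be raised and the gap is smaller than the two triggers suggest. The unit steps of protocol X were simulated with full adherence. Assumptions:

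- Randomisation Hb is 10 minus an exponential deficit, mean 0.5 or 1.0.
- The untransfused fall over days 1-3 has SD 0.7 or 0.3; measurement SD is 0.2.
- Each unit raises Hb by 1.0 gm/dl.

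For a mean fall of 0, 0.5 or 1.0 gm/dl the arm gap in nadir is 0.2-0.4, 0.6-0.7 or 1.0-1.1 gm/dl. With a rise per unit of 0.8 or 1.2, checked at the 0.5 fall, it is 0.62-0.69.

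**4. No true effect.** 1520 participants, 30% in both arms, nadir SD 1.0, 1000 trials per cell. Unmeasured severity has a log-odds or log-hazard of 0.3 or 0.8 per SD and correlates −0.3 or −0.5 with Hb. ORs and HRs are medians.

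| Gap (gm/dl) | Adjusted OR | Rejects at 5% | Rejects at 1% | Cox HR | Cox rejects at 5% |
|---|---|---|---|---|---|
| 0.3 | 1.03-1.12 | 6-15% | 1-5% | 1.03-1.12 | 7-23% |
| 0.6 | 1.06-1.24 | 8-44% | 2-24% | 1.05-1.25 | 9-61% |
| 1.0 | 1.10-1.44 | 11-84% | 4-62% | 1.09-1.44 | 13-93% |
| Pre-randomisation Hb instead | 1.00-1.01 | 4-6% | | 1.00-1.01 | 4-6% |

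Hand check: the spurious OR is roughly exp(log-odds per SD × |correlation| × gap/SD). At a gap of 1.0 the weak case gives exp(0.3·0.3·1.0) = 1.09 and the strong case exp(0.8·0.5·1.0) = 1.49. The simulated 1.44 is a little lower because the severity left over attenuates the logistic coefficient.

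With the rule-based nadir of step 3, the logistic model at 5% gives OR 1.04-1.26 (rejects 4-49%), 1.05-1.51 (7-91%) and 1.09-2.08 (13-100%) for the three falls. With pre-randomisation Hb it gives 0.98-1.01 (3-7%). The upper ends exceed the table's because the nadir SD there is about 0.5-0.7, so the same gap is larger in SD units.

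**5. A true effect of 30% against 22.5%.**

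- Half through the nadir, gaps 0.3-1.0: chi-square and the pre-randomisation Hb model reject 90-93% (OR 0.67-0.68). The nadir model gives OR 0.82-0.86 and rejects 22-33%. Hand check: exp(0.5·ln 0.677) = 0.82.
- All through the nadir, gaps 0.6-1.0: OR 1.00, rejects 4-5%. A separate simulation at N = 1444 gave OR 0.98-1.01 and 5-7%, against 0.67-0.68 and 90-92% with pre-randomisation Hb.
- Nadir effect set to the protocol's observational OR of 0.566 (unit not stated, assumed per gm/dl), gaps about 0.5 to 1.5: nadir-adjusted OR 0.90 to 1.54. With unmeasured severity added it was 1.04 to 2.32 against true direct-effect ORs of 0.86 to 1.49, so the direct effect is not recovered either.

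**6. Not simulated.** The quantile model, the secondary and tertiary endpoints' own event rates (the 1% column is for a 30% rate), and models with age, RCRI or interaction terms.

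**The case against.** The strongest reply is that the documents show a missing definition rather than a wrong analysis. SAP 7.1 lists nadir Hb with age and RCRI, both fixed before randomisation. The title of Table 17 puts the word baseline ahead of all three. The sections in protocol II and XVI.A justify event rates and do not define a model term, and the interval from surgery to randomisation is itself postoperative. This leaves a pre-randomisation reading open, but not the more natural one: SAP 7.4 and Tables 24-26 attach baseline to participant age only, and the protocol treats the nadir as a consequence of the arm.

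Second, the models are additional, and the adjusted null is openly conditional on the covariates. That stands and limits the severity. It does not make the coefficient interpretable as an effect of the strategy.

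Third, the null results run from almost no distortion to complete distortion, and nothing in the documents chooses between them. The planned age and RCRI terms would absorb some severity. This also stands: the figures show what can happen, not what to expect. That an effect acting wholly through the nadir disappears is true by construction. The direction of the bias needs only that assignment moves the nadir and that unmeasured severity both lowers it and raises risk.

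**Conclusion.** The concern holds. It should be fixed before analysis, but it does not threaten a confirmatory conclusion. The primary chi-square, the site-stratified Cochran-Mantel-Haenszel test, the unadjusted secondary and tertiary tests, the Wilcoxon test and the log-rank test are unaffected. Tables 24-26 test age of blood and are a separate matter.

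The conclusion depends on the post-randomisation reading, which is likelier but not certain. If a pre-randomisation value was intended, neither the estimand change nor the bias arises, and the defect is only that the plan does not say so. How large the distortion would be depends on the arm separation in nadir, its SD and the strength of unmeasured severity, none of which the documents give.

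**What to change.** In SAP 7.1-7.3, the time-to-event part of 7.4 and Tables 17, 19, 21, 23, 27 and 28, replace nadir Hb with the last Hb before randomisation, and align protocol XVI.E and Table 4. Name the variable explicitly, because SAP 6.4 lists pre-operative Hb as baseline while the SAP 5.3 rule points to the last pre-randomisation value. That value may also differ from the first one below the threshold: "A participant must be randomized within 24-hrs of the first postoperative Hb falling below 10 gm/dl".

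Keep post-randomisation nadir Hb for describing separation between the arms, or for a mediation analysis labelled exploratory. If the lowest value before randomisation was intended all along, one sentence giving that window is enough.

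The cost is wording and six table shells. Protocol X already has sites record "Pre- and post-randomization Hb levels", so no new data are needed.

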0.62, 95% CI: 0.33 to 1.14, $p=0.12$, Table 1). An intriguing observation of this study was that the event rate for the composite endpoint of death or ACS at 30 days was nearly 50% higher in the restrictive transfusion group (6.0% vs. 9.3%, Pearson's chi square test 0.052 on univariate analysis). After appropriate risk adjustment using propensity score matching this difference turned out to not be of statistical significance; however, the possibility remained that, in this patient population, a conservative transfusion strategy had a harmful effect that this observational study was simply too underpowered to conclusively demonstrate.

b) To address this possible power issue, [name] et al conducted a larger single institution study²⁹ with primary endpoint a composite of all-cause mortality, MI (defined according to the Third Universal Definition of MI), acute renal failure (defined as acute kidney injury stage 3 per RIFLE criteria), stroke, or coronary revascularization within 90 days after the index intervention. In this new analysis a total of 2509 PAD-related operations were included. The composite endpoint occurred in 28.7% of patients with nadir Hb between 6-9gm/dl and 12.1% of patients with nadir Hb >9 gm/dl ($p<0.001$). Increasing nadir postoperative Hb demonstrated a strong curvilinear relationship with the composite outcome (OR 0.72, 95% CI: 0.74 to 0.85). Patients at higher baseline cardiac risk (as captured by Revised Cardiac Risk Index -RCRI) were at higher risk for the composite outcome across all ranges of postoperative nadir Hb; RCRI class II (OR: 1.8, 95% CI: 1.29 to 2.40), class III (OR: 2.07, 95% CI: 1.45 to 2.94), and class IV (OR: 2.38, 95% CI: 1.58 to 3.49) were associated with progressively increasing odds of the CE compared to RCRI class I. (Figure 1).

FIGURE 1. Probability of the Composite Endpoint at Various Levels of the Postoperative Nadir Hb – Single institution data

[figure not shown]

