variable. We will also consider the Akaike Information Criterion statistic and the Schwartz Criterion statistic, both of which adjust the -2 log likelihood for the number of items in the model. Models that show lack of fit will be reconsidered for the inclusion of additional variables or use of alternate models with assumptions that are better met by the study data. One alternate model if the model fit is poor for logistic regression is a log-linear model. For logistic regression analysis, if the coefficient for intervention effect is significant (i.e., the confidence interval for the odds ratio does not include 1), then the null hypothesis of no intervention effect adjusting for other covariates in the final model will be rejected. The P value for testing each covariate coefficient in the model being zero will be based on Wald test (Table 17a-e). The primary analysis will be done in the ITT population. Additional analyses will be done in the mITT, No-Recent-Transfusion, Completers, and Per Protocol populations.

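### The statistic named for goodness-of-fit of the adjusted logistic models is an overall association test, so it cannot tell when a model should be reconsidered for lack of fit

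*SAP*

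**What the plan says.** SAP 7.1 makes the unadjusted Pearson chi-square in the ITT population the primary analysis. Logistic models adjusting for age, RCRI and nadir Hb are additional. On their fit it says: "We will assess goodness-of-fit using the statistic -2 log likelihood, which has a chi-square distribution under the null hypothesis" and it words that null as "that all the explanatory variables in the model are not associated with the outcome". Protocol XVI.E.2 has the same rule: "which has a chi-square distribution under the null hypothesis that all the explanatory variables in the model are zero".

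Four further statements in SAP 7.1 bear on the point:

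- A separate check: "Assumptions of the model including linearity in the logit of the composite event risk for continuous variables will be checked". The Protocol section has no such sentence. No method, threshold or consequence is given.
- Two more measures: "We will also consider the Akaike Information Criterion statistic and the Schwartz Criterion statistic".
- The consequence: "Models that show lack of fit will be reconsidered for the inclusion of additional variables or use of alternate models".
- A named alternative: "One alternate model if the model fit is poor for logistic regression is a log-linear model".

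SAP 7.2 and 7.3 refer the secondary and tertiary logistic models back to this method. The shell for SAP Table 17 has one row each for age and nadir Hb, which implies a single linear term for each.

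**The concern.** A goodness-of-fit test takes as its null that the model describes the data. The null worded in both documents is that nothing in the model predicts the outcome. Rejecting it shows that at least one term matters. It does not show that the terms have the right shape or that predicted and observed risks agree. A poorly shaped model with one strong predictor will reject it; a correct model with weak predictors or few events may not.

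The mislabelling matters because an action follows. Models judged to fit poorly are to be reconsidered, and the adjusted treatment effect is then tested in whatever the final model is. The named statistic carries no information about when that should happen. Treatment is itself one of the explanatory variables, so the statistic also looks better when treatment has an effect.

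**Working it through.** **Design figures.** The plan gives no figure for model fit, so its sample size was reproduced to set the simulation. With 30% and 22.5% (SAP 4.5), two-sided alpha 0.05 and 90% power, the mean rate is 26.25% and

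n per arm = [1.960 × √(2 × 0.2625 × 0.7375) + 1.2816 × √(0.30 × 0.70 + 0.225 × 0.775)]² / 0.075² = (1.2196 + 0.7945)² / 0.005625 ≈ 721.2, rounded up to 722.

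The total is 1444, and 1444 / 0.95 = 1520. Both match the SAP.

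**The statistic as worded.** Under a null of no association, the quantity with a chi-square distribution is G = 2 × (logL of the fitted model − logL of the intercept-only model). With treatment (1), age (1), RCRI in four classes (3) and Hb (1), it has 6 degrees of freedom.

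**Simulation.** 1000 trials per scenario, N = 1520, overall event rate 26.25%. Assumed log odds ratios were 0.3 per SD of age, 0.3 per RCRI class and −0.4 per SD of Hb, with the planned treatment effect. The misfit scenario adds an Hb-squared term of 0.35 that the fitted model leaves out. The third scenario has no treatment or covariate effects, so the fitted model is again correct. Rejection rates at 5%:

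| Test | Model correct | Hb curvature omitted | No effects (model correct) |
|---|---|---|---|
| G, 6 df (the stated null) | 100% | 100% | 4.1% |
| Likelihood-ratio test of Hb-squared, 1 df | 4.2% | 100% | 5.4% |
| Hosmer-Lemeshow, 10 groups | 5.3% | 64.8% | 3.6% |
| Raw −2 logL against chi-square on 1520 − 7 = 1513 df | 87.2% | 86.7% | 100% |

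G gives the same answer for the correct and the misfitted model. The SAP does not say which result counts as lack of fit. If it is a non-significant G, both models pass and the correct model with no effects nearly always fails. If it is a significant G, both fail. Neither reading works.

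The last row covers the other possible meaning, −2 log likelihood as a residual deviance. That contradicts the stated null and is not valid for ungrouped binary data: it rejects correct and misfitted models about equally often.

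**Rare components.** One primary, four binary secondary and five tertiary endpoints make 1 + 4 + 5 = 10 binary endpoints using this method, each in five populations. Protocol Table 2 gives coronary revascularization as 0.3% to 0.4%; 1520 × 0.0035 ≈ 5 events. Protocol II puts stroke at about 1%; 1520 × 0.01 ≈ 15 events. In correctly specified models at these rates, with the covariate effects above at full and at half size, G was non-significant in 80% to 91% of trials for revascularization and 61% to 81% for stroke. A repeat run moved these limits by 2 to 6 percentage points. Few events alone can therefore make a correct model look as if it fits poorly.

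**The case against.** The strongest reply is that the SAP does not rely on this statistic alone. The sentence on linearity in the logit addresses the very misfit simulated here. AIC and the Schwarz criterion can also favour a curved Hb model once one is fitted: with an Hb-squared term of 0.35 both did so in 100% of 400 simulated trials, and at 0.15 AIC did so in about 95%. This stands. It is why the point is confined to the named fit statistic. It does not rescue that statistic: the linearity check has no method or consequence, and the information criteria only rank the models someone has chosen to fit.

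A reader might infer more than the documents support:

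- *That this statistic decides whether the model changes.* No cut-off is given, other measures are considered, and the text says only that models will be reconsidered. Where G is almost always significant, its natural reading as an association test would trigger no change at all.
- *That the plan as a whole lets wrong models through.* The linearity check may catch them; the documents do not allow a judgement either way.
- *That models will be changed after the treatment effect is known.* Neither document states the order of these steps.
- *That the adjusted treatment effect would be seriously distorted.* In simulation, omitting the strong curvature moved the mean treatment odds ratio from about 0.68 to 0.69 with Hb balanced between arms, and to 0.71 with arms 1 SD apart.
- *That curvature in the logit is already established.* Protocol II reports that nadir Hb "demonstrated a strong curvilinear relationship with the composite outcome", with a single odds ratio and a plot of probability. A relation linear in the logit is already curved on the probability scale. Curvature is plausible, not shown.

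**Conclusion.** The point holds for the adjusted logistic analyses. By the documents' own wording, the named goodness-of-fit statistic is an overall association test, and it cannot be the criterion for a rule about lack of fit. This follows from the hypothesis tested. The simulated percentages rest on assumed effect sizes and illustrate it; the Hosmer-Lemeshow detection rate in particular would change with them.

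The consequence is small. The primary Pearson chi-square, its alpha and the sample size are unaffected, and the simulated shift in the adjusted odds ratio is about 0.01 to 0.03. The reach is wider than the primary endpoint, because the secondary and tertiary logistic models inherit the rule and some components are rare.

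**What to change.** In SAP 7.1, with the same correction in Protocol XVI.E.2 or a note in the SAP that it departs from the Protocol:

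1. Call the −2 log likelihood test an overall association test and remove it as the fit criterion.
2. Say how the planned linearity check is done: a quadratic or spline test for age and for Hb, and what follows from the result.
3. Report calibration descriptively, as observed against expected events by decile of predicted risk. With 64.8% detection in the misfit scenario, a Hosmer-Lemeshow p-value should not act as a gate.
4. Fix the covariates and functional form of the adjusted model before unblinding. Report any model refitted because of poor fit as a sensitivity analysis only.

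The cost is SAP wording. No new data are needed, and SAP 5.1 places the final analysis after the SAP is finalized and approved.
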